# tablets per day: 1 tablet per day: 1mg, 2mg, 4mg, 6mg, 8mg, 10mg 2 tablets per day: 12mg, 16mg 3 tablets per day: 24mg																																																																																			
Duration of Exposure Record	Under Compliant	Compliant	Over Compliant																																																																																
1 – 14 days	< 1 dose	1 dose	> 1 dose																																																																																
15 – 42 days	< 1 dose	1 or 2 doses	> 2 doses																																																																																
43 – 70 days	< 2 doses	2 or 3 doses	> 3 doses																																																																																
71 – 98 days	< 3 doses	3 or 4 doses	> 4 doses																																																																																
99 – 126 days	< 4 doses	4 or 5 doses	> 5 doses																																																																																
Etc.																																																																																			
Duration of Exposure Record	Under Compliant	Compliant	Over Compliant																																																																																
1 – 7 days	< 1 dose	1 dose	> 1 dose																																																																																
8 – 21 days	< 1 dose	1 or 2 doses	> 2 doses																																																																																
22 – 35 days	< 2 doses	2 or 3 doses	> 3 doses																																																																																
36 – 49 days	< 3 doses	3 or 4 doses	> 4 doses																																																																																
50 – 63 days	< 4 doses	4 or 5 doses	> 5 doses																																																																																
64 – 77 days	< 5 doses	5 or 6 doses	> 6 doses																																																																																
78 – 91 days	< 6 doses	6 or 7 doses	> 7 doses																																																																																
92 – 105 days	< 7 doses	7 or 8 doses	> 8 doses																																																																																
Etc.																																																																																			

Exposure and Compliance			
○ Darbe Every Week Exposure Records: Based on Number of Doses Given			
Duration of Exposure Record	Under Compliant	Compliant	Over Compliant
1 – 3 days	< 1 dose	1 dose	> 1 dose
4 – 10 days	< 1 dose	1 or 2 doses	> 2 doses
11 days	< 1 dose	1 or 2 or 3 doses	> 3 doses
12 – 17 days	< 2 doses	2 or 3 doses	> 3 doses
18 days	< 2 doses	2 or 3 or 4 doses	> 4 doses
19 – 24 days	< 3 doses	3 or 4 doses	> 4 doses
25 days	< 3 doses	3 or 4 or 5 doses	> 5 doses
26 – 31 days	< 4 doses	4 or 5 doses	> 5 doses
32 days	< 4 doses	4 or 5 or 6 doses	> 6 doses
33 – 38 days	< 5 doses	5 or 6 doses	> 6 doses
39 days	< 5 doses	5 or 6 or 7 doses	> 7 doses
40 – 45 days	< 6 doses	6 or 7 doses	> 7 doses
46 days	< 6 doses	6 or 7 or 8 doses	> 8 doses
47 – 52 days	< 7 doses	7 or 8 doses	> 8 doses
53 days	< 7 doses	7 or 8 or 9 doses	> 9 doses
Etc.			

- Compliance will be summarized for the following time periods: Day 1 - < Week 28, Week 28 - < Week 52, Week 28 - < End of Treatment, and Day 1 - < End of Treatment (Overall compliance).
- Within each period, the percentage of time that a subject spent in each of the 3 categories above or with missing compliance data will be determined and will be based on the durations of each record within the period.
- A subject's compliance category will be the category that corresponds to the highest percentage of total time. In the unlikely event of a tie, the lower compliance category will be chosen (i.e., in a tie between under and compliant, under is chosen; in a tie between compliant and over, compliant is chosen; and in a tie between under and over, under is chosen; in a tie with missing, missing is chosen).

10.6.3. Efficacy

10.6.3.1. Hemoglobin Endpoints

Hemoglobin Values
Central Laboratory and HemoCue Hgb Values

 ● When source of Hgb measurement is not specified: 
 ○ For reporting purposes, central laboratory Hgb values will be used, unless otherwise specified. However, if a central laboratory Hgb value is missing, a corresponding non-missing HemoCue Hgb value will be used. This approach will

Hemoglobin Values

be used for the co-primary Hgb analysis.
 
 Some displays may be created for either central laboratory Hgb values only or HemoCue Hgb values only. The central laboratory summary will be considered the primary summary in this case.
Evaluable Hemoglobin Values

 Evaluable Hgb values are on-treatment Hgb values (see Section 10.4.1) that are not taken within the 8 weeks following a red blood cell transfusion, a whole blood transfusion, or a non-randomized ESA treatment which occurs on or after the randomization date. Red blood cell transfusions, whole blood transfusions and non-randomized ESA treatments occurring on or after the randomization date are identified by comparing the start and stop date of the respective transfusion or ESA concomitant medication record to the randomization date.
Imputed Hemoglobin Values

 For each missing value between baseline to Week 52 (inclusive), 200 imputed values will be generated using the multiple imputation method (see Section 7.1.2). The average of these 200 imputed values will be used as the value for this missing value in the summary tables and figures. For co-primary efficacy Hgb analysis and the corresponding subgroup analyses using all available observed and imputed Hgb values (on and off-treatment), Rubin's rules [Rubin, 1987] will be used to combine results of the imputed datasets using SAS PROC MIANALYZE procedure.
EP Hemoglobin Value for Co-primary Hgb Analysis

 For each subject, the mean of all available (on and off treatment) Hgb values during the EP (See Section 10.6.1) including any imputed and unscheduled Hgb values that were taken during this time period. Should the assessment dates for Hgb values from the Early Treatment Discontinuation visit and the End of Study visit fall within the EP, then these values will be included as unscheduled Hgb values. Hgb values from the Follow-up visit will not be included in the EP mean.
EP Hemoglobin Value for While On-Treatment Evaluable Hgb Supportive Analysis

 For each subject, the mean of all evaluable Hgb values during the EP (See Section 10.6.1) including any evaluable unscheduled Hgb values that were taken during this time period. Should the assessment dates for Hgb values from the Early Treatment Discontinuation visit and the End of Study visit fall within the EP, then these values will be included as unscheduled Hgb values. Hgb values from the Follow-up visit will not be included in the EP mean.
EP Hemoglobin Value for Alternative EP Supportive Analyses

 For each subject, the mean of all Hgb values during the Alt. EP (See Section 10.6.1) including any imputed and unscheduled Hgb values that were taken during this time period. This analysis will be conducted using all available (on and off treatment) Hgb values and separately using evaluable Hgb values only. Should the assessment dates for Hgb values from the Early Treatment Discontinuation visit and the End of Study visit fall within the Alt. EP, then these values will be included as unscheduled Hgb values. Hgb values from the Follow-up visit will not be included in the Alt. EP mean.
Use of Unscheduled Hemoglobin Values and Multiple Hgb Values on the Same Date

 The scenarios outlined below provide guidance on the use of unscheduled Hgb values and

Hemoglobin Values

- multiple Hgb values occurring on the same date. Each row represents a single calendar date.
- Rows outlining scenarios where there is at least one central lab Hgb and at least one HemoCue Hgb on the same date apply only for the derivation of Hgb values to be used in the co-primary Hgb analysis, where central lab values are used if they are available and if the central lab value is missing, then a corresponding non-missing HemoCue Hgb value is used.
 - Rows outlining scenarios involving combinations of scheduled and unscheduled Hgb values of the same type apply to all Hgb summaries and analysis.

Scheduled Central Lab Hgb Value	Unscheduled Central Lab Hgb Value	Scheduled HemoCue Hgb Value	Unscheduled HemoCue Hgb Value	Value to Use	Type/Label
x				Scheduled central lab Hgb value	Scheduled visit
	x			Unscheduled central lab Hgb value	Unscheduled
		x		Scheduled HemoCue Hgb value	Scheduled visit
		multiple ¹		Average of scheduled HemoCue Hgb values	Scheduled visit
			x	Unscheduled HemoCue Hgb value	Unscheduled
	multiple			Average of unscheduled central lab Hgb values	Unscheduled
			multiple	Average of unscheduled HemoCue Hgb values	Unscheduled
x	x			Average of central lab Hgb values	Scheduled visit
x		x		Scheduled central lab Hgb value	Scheduled visit
x			x	Scheduled central lab Hgb value	Scheduled visit
	x	x		Unscheduled central lab Hgb value	Unscheduled
	x		x	Unscheduled central lab Hgb value	Unscheduled
		x	x	Average of HemoCue Hgb values	Scheduled visit

1: The dose adjustment algorithm will require sites to obtain two HemoCue Hgb values at some visits.

Time In Range

Time in Range During the EP

- Number of days that a subject's evaluable Hgb is within the analysis range of 10-11.5 g/dL inclusive during the EP (See Section 10.6.1), including any unscheduled evaluable Hgb values that were taken during this time period.
- Use of unscheduled Hgb values follows the scenarios for unscheduled and multiple Hgb values.
- Linear interpolation is used to estimate Hgb between visits, accounting for any intermittent missing values [Rosendaal, 1993].

Percent Time in Range During the EP

- Time in Range During the EP / [Earlier of (Date of the last evaluable Hgb value, Week 52 visit date) – Later of (Date of the first evaluable Hgb value that between Week 16 and Week 52

Time In Range

inclusive, Week 28 visit date)]
 
 Note: Percent time in/below/above range during the EP is only defined for subjects with a Treatment Stop Date that is on or after their Week 28 visit date, and have at least two evaluable Hgb values on different days, where at least one evaluable Hgb value is contained within the EP and another evaluable Hgb value occurs within the range of the Week 16 visit through 4 weeks following the Week 52 visit, inclusive.
Time in Range During the MP

 Number of days that a subject's evaluable Hgb is within the analysis range of 10-11.5 g/dL inclusive between Weeks 28 and End of Study inclusive, including any unscheduled evaluable Hgb values that were taken during this time period. Linear interpolation is used to estimate Hgb between visits, accounting for any intermittent missing values [Rosendaal, 1993].
Percent Time in Range During the MP

 Time in Range During the MP / [Earlier of (Date of the last evaluable Hgb value, End of study date)– Later of (Date of the first evaluable Hgb value that is on or after week 16, Week 28 visit date)] Note: Percent time in/below/above range during the MP is only defined for subjects with a Treatment Stop Date that is on or after their Week 28 visit date, and have at least two evaluable Hgb values on different days, where at least one evaluable Hgb value is contained within the MP and another evaluable Hgb value occurs within the range of the Week 16 visit through the Treatment Stop Date + 1 day.

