
 ● All available observed Hgb values (on and off-treatment) will be summarized using mean, standard deviation, minimum, P25, median, P75 and maximum at each visit by treatment group. In addition to scheduled visits, the baseline value and mean MP, mean EP, mean Alt EP, and end of treatment values will be included (see Section 10.6.3). This summary is repeated by current ESA use at randomization. 
 ○ This summary of Hgb will also be repeated for visits up to and including Week 52, using the data used for the primary Hgb analysis (i.e., including imputed values (see Section 10.6.3)), and by current ESA use at randomization. ● All available observed Hgb change from baseline values (on and off-treatment) will also be summarized using mean, standard deviation, minimum, P25, median, P75, and maximum at each post-baseline visit, including the mean MP, mean EP, mean Alt EP, and end of treatment values (see Section 10.6.3). This summary is repeated by current ESA use at randomization. 
 ○ This summary of Hgb will also be repeated for visits up to and including Week 52, using the data used for the primary Hgb analysis (i.e., including imputed values (see Section 10.6.3)), and by current ESA use at randomization. ● The number and percentage of subjects with imputed data in the primary Hgb analysis will be provided by treatment group. The number and percentage of subjects by reason for data imputation will be provided. Reasons include: intermittent missing Hgb values, death before Week 28, death during Weeks 28 – 52, investigator site closed before Week 28, investigator site closed during Weeks 28-52, lost to follow-up before Week 28, lost to follow-up during Weeks 28 – 52, consent withdrawn before Week 28, consent withdrawn during Weeks 28 – 52, EOS visit occurred before Week 28, EOS visit occurred during Weeks 28-52, and other monotone missing Hgb values. Subjects will be further classified as either having observed all 7 scheduled EP Hgb values, having observed a partial schedule of EP Hgb values, having observed no scheduled EP Hgb values with at least one unscheduled EP Hgb value, or having observed no EP Hgb values, scheduled or unscheduled. For subjects with partial scheduled EP Hgb values, both the pattern of imputed data (intermittent, monotone) and the amount of imputed data (1 – 6 scheduled Hgb values missing) will be summarized. For subjects with partial scheduled EP Hgb values and a monotone imputed data pattern, the reason for the monotone imputed scheduled EP Hgb values will be provided. Reasons include: death during Weeks 28-52, investigator site closed during Weeks 28-52, lost to follow-up during Weeks 28 – 52, consent withdrawn during Weeks 28 – 52, EOS visit occurred during Weeks 28-52, and other monotone imputed Hgb values. And for summaries of the amount of missing scheduled EP Hgb values, the presence or absence of additional unscheduled EP Hgb values will be summarized.

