A box plot of evaluable Hgb change at Week 2 from baseline, by baseline clopidogrel co-administration and treatment group will be produced. Baseline clopidogrel co-administration is defined as subjects who use clopidogrel at randomization. Hemocue Hgb will be used in this figure, since only Hemocue Hgb is available at Week 2. This box plot will be repeated at Week 4 using evaluable Hgb, by baseline clopidogrel co-administration and treatment group.

A box plot of 4-week changes in evaluable Hgb after starting clopidogrel will also be produced by treatment for new clopidogrel users, who started clopidogrel after randomization, during the on-treatment state for concomitant medications (see Section 10.4.1). The 4-week change in evaluable Hgb will be estimated by calculating the change at the first visit after starting clopidogrel, from the previous visit at least 4 weeks before. The first visit after starting clopidogrel is defined as the first visit (scheduled or unscheduled) after clopidogrel start that was at least two weeks after the start date of clopidogrel.

COVID-19 Analyses

The following COVID-19 related displays will be provided.

A summary of the number and percentage of subjects for the following assessments will be produced: Case Diagnosis, COVID-19 Test performed, and Results of the COVID-19 test.

Summaries of characteristics of COVID-19 AEs will include the number, percentage of subjects having at least one occurrence, the outcome, maximum intensity, and the duration of the AE summarized by treatment group. For each count, a subject will be summarized as follows:

- Outcome: The subject will be counted within a category if there is at least one specific AE in that category.
- Maximum intensity: The specific AE with the maximum intensity will be counted for this purpose. For example, a subject will be counted in the ‘severe’ category if there is at least one specific AE with severe intensity. A subject will be counted in the ‘moderate’ category if there is at least one specific AE with moderate intensity and there is no specific AE with severe intensity.
- Duration of the occurrence (days): AE resolution date – AE onset date/AE worsening date + 1 for the occurrence

A summary of the number and percentage of subjects with COVID-19 symptoms will be produced.

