10.5.2. Baseline Definition & Derivations

10.5.2.1. Baseline Definitions

For all endpoints (except as noted) the baseline value will be the latest non-missing pre-dose assessment on or before the randomization date. This is generally expected to be the pre-dose value from the Day 1 visit, although such values may be missing.

Parameter	Study Assessments Considered As Baseline			Baseline Used in Data Display
	Screen Week -8	Run-in Week -4	Day 1 (Pre-Dose)	
Efficacy				
Hgb			X	Randomization Date
Iron parameters			X	Randomization Date
Safety				
BP parameters, HR and weight ¹			X	Randomization Date
Lipid parameters, renal function parameters, clinical chemistry, hematology, other laboratory and hepatobiliary (liver) tests			X	Randomization Date

Parameter	Study Assessments Considered As Baseline			Baseline Used in Data Display
	Screen Week -8	Run-in Week -4	Day 1 (Pre-Dose)	
PRO				
SF-36 domain and component scores			X	Randomization Date
EQ-5D-5L & VAS			X	Randomization Date
PGI-S			X	Randomization Date
CKD-AQ			X	Randomization Date
WPAI-ANS-CPV			X	Randomization Date

[1]: For subjects who start dialysis during the study, the baseline vital sign values will be used as baseline values for pre- and post- dialysis vital sign displays and baseline weight will be used as the baseline dry weight value.

NOTES:

- Unless otherwise stated, the mean of replicate assessments at any given time point will be used as the value for that time point.

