10.5.2.2. Derivations and Handling of Missing Baseline Data

Change from Baseline

Definition	Reporting Details
Change from Baseline	= Post-Baseline Visit Value – Baseline

NOTES:

- Unless otherwise specified, the baseline definitions specified in Section 10.5.2 Baseline Definitions will be used for derivations for endpoints / parameters and indicated on summaries and listings.
- Unless otherwise stated, if baseline data is missing no derivation will be performed and the change from baseline value will be set to missing.
- The baseline definition will be footnoted on all change from baseline displays.

Percent Change from Baseline

Lipid parameters will be log-transformed and the percent change from baseline will be reported. Other endpoints may also be log-transformed if deemed appropriate.

To calculate a geometric mean for baseline measurement or at a specified timepoint, the following steps are used:

1. Log-transform the data points
2. Calculate the mean and standard error (SE) of the log-transformed data
3. Exponentiate the mean, (if required, the mean – SE, mean + SE) and the endpoints of the confidence interval back to the original scale in order to obtain the geometric

mean, (the geometric mean – SE, the geometric mean + SE) and the confidence interval for the geometric mean.

4. Coefficient of variation will be calculated as

$$CV = \sqrt{\exp(\text{Var}_{\log\text{scale}}) - 1} \times 100\%$$

To calculate a geometric mean for the ratio of a specific timepoint to baseline (expressed as a percent change from baseline), the following steps are used:

1. Log-transform the data at both the baseline and the specified timepoint
2. For each subject, calculate a change from baseline using the log-transformed data
3. Calculate the mean and standard error (SE) of change from baseline using the log-transformed data
4. Exponentiate the mean, (if required, the mean – SE, the mean + SE), back to the original scale and then subtract 1, then multiply everything by 100% in order to express the geometric mean, (the geometric mean – SE, the geometric mean + SE) as the percent change from baseline.

So, geometric mean for percent change from baseline =

$$[\text{Exp}(\sum \{ \log(\text{value at specified time point}_i) - \log(\text{baseline value}_i) \} / n) - 1] \times 100,$$

Where i = subject, n = total number of subjects, and \sum represents the sum over all subjects.

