10.6.4.4. Adverse Events

Adverse Events
AEs of Special Interest

Adverse events of special interest are classified as follows:
 
 • Thrombosis and/or tissue ischemia secondary to excessive erythropoiesis • Cardiomyopathy • Pulmonary artery hypertension • Cancer-related mortality and tumor progression and recurrence • Esophageal and gastric erosions • Proliferative retinopathy, macular edema, choroidal neovascularization • Exacerbation of rheumatoid arthritis • Worsening of hypertension

Adverse Events

Potential AESIs will be identified through a pre-defined terms of interest process in which pre-defined lists of AE preferred terms corresponding with each AESI will be used to identify events considered to be potential AESIs. Sites will be prompted via query to complete any necessary additional information for these AESIs in the eCRF.

For the category of thrombosis and/or tissue ischemia secondary to excessive erythropoiesis, after the terms of interest list has been applied, the additional Hgb criteria described below will be applied to identify only those events that are considered to be secondary to excessive erythropoiesis as meeting the AESI definition for thrombosis and/or tissue ischemia secondary to excessive erythropoiesis.

Thrombosis and tissue ischemia events will be considered to be secondary to excessive erythropoiesis if during the window of [AE start date – 30 days, AE start date +15 days] any one of the following 3 events occurs:

- Any Hgb value \geq 13 g/dL (measured pre-dialysis)
- Hgb increase $>$ 2 g/dL over 2 weeks (+1 week)
 - Note: for programming purposes, a +1 week window is applied, corresponding to the allowable visit window, to look for increases $>$ 2 g/dL over 3 weeks
- Hgb increase $>$ 4 g/dL over 4 weeks (+1 week)
 - Note: for programming purposes, a +1 week window is applied, corresponding to the allowable visit window, to look for increases $>$ 4 g/dL over 5 weeks

To identify Hgb increases that meet the increase criterion above, all Hgb values taken within [AE start date – 58 days, AE start date + 15 days] will be identified. This corresponds to identifying Hgb values that occurred 4 weeks before the [AE start date – 30 days, AE start date +15 days] window of interest. HemoCue Hgb and central laboratory Hgb values will then be evaluated separately to identify increases, so that HemoCue and central laboratory Hgb values are not compared to each other to identify an increase.

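### In the by-visit hemoglobin displays the Week 2 change from baseline is normally HemoCue minus central laboratory, so the within-arm Week 2 mean includes any difference between the two methods

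*SAP*

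**What the plan says.** Section 10.6.3.1 sets the source rule for displays that do not name a method. Central laboratory values come first, and "if a central laboratory Hgb value is missing, a corresponding non-missing HemoCue Hgb value will be used". The table of same-day scenarios in that section adds that a scheduled HemoCue value standing alone is used and carries the scheduled visit label.

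Section 10.5.2.1 defines baseline: "the baseline value will be the latest non-missing pre-dose assessment on or before the randomization date". It expects this to be the Day 1 value. Section 10.5.2.2 defines change from baseline as "Post-Baseline Visit Value – Baseline", and no separate HemoCue baseline is defined.

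The schedule in Section 10.2.1.1 marks HemoCue at every visit from screening to Week 52. The hematology row, which carries the central hemoglobin, is marked on Day 1, at the full visits and at Week 52. It is marked for hemoglobin alone at the abbreviated visits and is empty at Week 2. Section 8.2.9 confirms this for its clopidogrel box plot: "Hemocue Hgb will be used in this figure, since only Hemocue Hgb is available at Week 2".

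Section 7.1.2.5 then states: "All available observed Hgb change from baseline values (on and off-treatment) will also be summarized". The summary covers each post-baseline visit, and the matching line plot covers each scheduled visit. Week 2 is not excepted in either.

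**The concern.** Read together, these rules change the measurement method at one visit while keeping the baseline fixed. At Week 2 the displayed change is a point-of-care value minus a laboratory value. From Week 4 it is normally laboratory minus laboratory.

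Week 2 is the first point after treatment starts, and a reader of the plot may well take it as the initial hemoglobin response in each arm. If the two methods differ systematically, part of that apparent early rise or fall, and of the bend between Week 2 and Week 4, comes from the method. Nothing in the table or plot would show this.

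**Working it through.** The SAP gives no figure for agreement between the methods, so there is nothing to reproduce. The check is to follow the rules and write out what they yield.

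**Source at each visit**

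| Visit | Central value scheduled | HemoCue scheduled | Value used |
|---|---|---|---|
| Day 1 (baseline) | yes | yes | central |
| Week 2 | no | yes | HemoCue |
| Week 4 onward, to Week 52 | yes | yes | central |

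Schedule: Section 10.2.1.1. Selection: Section 10.6.3.1.

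**Algebra.** Let b be the mean HemoCue-minus-central difference, taken as constant, and let c2 and c4 be the true mean changes at Weeks 2 and 4 within an arm.

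- Displayed Week 2 change = (true Week 2 value + b) - central baseline = c2 + b.
- Displayed Week 4 change = c4.
- Displayed step from Week 2 to Week 4 = c4 - (c2 + b) = (c4 - c2) - b.
- Displayed difference between arms at Week 2 = (c2 in one arm + b) - (c2 in the other arm + b), so b cancels.

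**Illustration with assumed values.** Neither figure comes from the document. Take a true two-week rise of 0.3 g/dL.

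| Assumed b (g/dL) | Displayed Week 2 change (g/dL) |
|---|---|
| -0.5 | 0.3 - 0.5 = -0.2 |
| -0.2 | 0.3 - 0.2 = +0.1 |
| 0 | +0.3 |
| +0.2 | 0.3 + 0.2 = +0.5 |
| +0.5 | 0.3 + 0.5 = +0.8 |

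**With a Day 1 HemoCue baseline.** Week 2 change = (true Week 2 value + b) - (true baseline + b) = c2. A constant b drops out.

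**Exceptions under the rules as written.** A subject without a central baseline value has a HemoCue baseline, and the Week 2 change is then already HemoCue minus HemoCue. An unscheduled central sample on the Week 2 date displaces the HemoCue value and is labelled unscheduled, so it does not appear as Week 2. The mixed subtraction therefore applies to nearly all subjects, not to every one.

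**Displays of absolute hemoglobin.** The by-visit value tables and plots in Section 7.1.2.5, the dosing-algorithm profiles in Section 8.1.2.2 and the phosphate-binder overlay in Section 8.1.3 subtract no baseline. In these, Week 2 is a change of method along the curve, not a mixed subtraction.

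**The case against.** The strongest reply is that nothing inferential depends on Week 2, and this is correct. The co-primary endpoint averages Weeks 28 to 52. The Week 52 repeated-measures model in Section 8.1.1.2 leaves out the stabilization period. In the imputation model of Section 7.1.2.5, where Week 2 can serve as an earlier scheduled value, the regression intercept absorbs a constant offset. A reader might infer that non-inferiority on hemoglobin is at risk; it is not.

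A reader might also infer that the plan breaks a prohibition of its own, because Section 10.6.4.4 handles the methods separately "so that HemoCue and central laboratory Hgb values are not compared to each other to identify an increase". That rule serves one purpose: flagging a rise in an individual subject around a thrombosis or ischemia event. It is not a general ban, and Section 10.6.3.1 openly adopts mixed sourcing. What can be said is that single-method handling is the plan's own practice where short-term change is the question: in the criterion just cited, in the Week 2 box plot of Section 8.2.9, and in Section 8.1.2.2, where the two-week rise and fall criteria use HemoCue and the central-laboratory tables start at Week 4. Those Section 8.1.2.2 tables already give a single-method view of early change, which further limits what is lost.

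Nor is the assessment of the updated dosing algorithm compromised. Week 2 is normally HemoCue under both algorithms and in both arms, so a constant offset cancels in that comparison. Only a kink within each curve remains.

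Finally, missing in the source rule could be read as scheduled but not obtained, which would leave Week 2 blank. The SAP does not say so, and the scenario row for a lone scheduled HemoCue value points the other way.

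**Conclusion.** The point holds for the descriptive change-from-baseline tables and line plots of Section 7.1.2.5. For nearly all subjects the Week 2 change is HemoCue minus central laboratory. The within-arm Week 2 mean is shifted by the full systematic difference between the methods, and the Week 2 to Week 4 step by the same amount in the opposite direction.

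The document does not give the size of that difference, and it could be close to zero. It would therefore go too far to say that the displayed early change is wrong; the supportable statement is that it cannot be separated from a method effect. The cancellation between arms and between algorithms assumes the same constant offset in each group. Severity is low: this is a presentational correction, with no effect on the co-primary result.

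**What to change.** In Section 7.1.2.5, or as a Week 2 exception in Section 10.5.2, state that change from baseline at Week 2 is computed from the Day 1 HemoCue value, and label that visit as HemoCue in the table and on the plot.

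In displays of absolute hemoglobin by visit that include Week 2 (Section 7.1.2.5, the dosing-algorithm profiles in Section 8.1.2.2 and the phosphate-binder overlay in Section 8.1.3), add a label or footnote saying that the Week 2 value is HemoCue, so that a change of method is not read as a change in hemoglobin.

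The cost is SAP wording and minor programming. Day 1 HemoCue is already scheduled, so no new data are needed, and no model or hypothesis test changes.
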